## Statistical Plan

A descriptive analysis of demographic data and injury characteristics will be conducted using a frequency distribution for categorical data and means for continuous variables. These data will be used to characterize general information about the study population. Sample size and data distribution will guide statistical analysis. If data assumptions are achieved, for Aim 1, we will determine the effects of tsDCS during walking using two-way repeated measures ANOVAs. The within factors will be time (before or at the end of walking bout) and stimulation (higher or lower dosage tsDCS). We will then examine the interaction effect to determine differences in the changes during walking with the two dosages of tsDCS. For Aim 2, mixed method ANOVAs will be used to determine the effects of tsDCS dosage during locomotor training. The within factor will be time (pre- or post-test) and between factor will be group (higher or lower dosage tsDCS). We will then examine the interaction effect to determine differences in the improvement during locomotor training with the two dosages of tsDCS. Differences will be considered significant at p<.05. Data will be analyzed using professional statistical software.

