## 5. Specific Aims:

Specific Aim 1 (Cross-sectional): To test the hypothesis that tsDCS applied during walking will improve muscle activation and lower limb kinematics in adults with chronic ISCI. A random order, double blind cross-over study will be conducted across two test sessions to compare the immediate effects of two dosages of tsDCS during walking. The higher dosage of tsDCS aligns with previous research protocols, while the lower dosage can be effectively be viewed as sham stimulation. Bilateral lower extremity surface electromyograms and 3-dimensional kinematics will be recorded. Outcomes will be changes in muscle activation amplitude and timing, and hip joint excursion during walking. tsDCS induced changes in spinal excitability, as measured by tests of the Hoffman reflex (H-reflex), also will be assessed.

Specific Aim 2 (Interventional): To test the hypothesis that tsDCS applied during 16 sessions of locomotor training will improve functional walking outcomes. Participants will be randomized to receive 16 sessions of tsDCS at one of the two dosages with locomotor training. Primary functional outcomes will include standardized clinical tests of walking speed and endurance. Secondary outcomes will include quantifying changes in muscle activation amplitude and timing, lower limb kinematics and the cortical control of walking during over ground walking.

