## Study Procedures Overview

For Aim 1 (immediate effects of tsDCS), participants will complete two separate testing sessions, presented in random order, that involve up to 30 minutes of tsDCS at one of the two dosages while walking. We will assess changes in muscle activity, kinematics and spinal excitability before and at the end of the period of walking. The two sessions will last about 3 hours and no longer than 6 hours and will take place at least 48 hours apart to allow for wash-out of stimulation effects.

For Aim 2 (effects of tsDCS applied with locomotor training), participants will be randomized to receive 16 sessions of locomotor training with tsDCS at one of the two dosages. Each intervention session will last about 1 hour and no longer than 2.5 hours. Before and after the 16-session intervention (i.e., at baseline and post intervention), we will assess functional outcomes through standardized clinical tests of walking speed and endurance, as well as changes in muscle activity, kinematics and spinal excitability. We will also examine the participant's spasticity and pain using standardized assessments. Each assessment session will last about 3 hours and no longer than 6 hours.

Overall, the testing and intervention procedures of this study will be as follows (see Fig. 1 for details):

- 1. Aim 1's first visit will consist of clinical testing and collection of basic demographic information (see Information Sources and Identifier attachments for demographics form) to characterize the participant. Neuromechanical assessments of walking and reflex testing prior to and after 30 minutes of tsDCS at one of the two dosages delivered while walking on a treadmill will be conducted.
- 2. Aim 1's second visit will involve identical procedures for stimulation and neuromechanical assessments as compared to visit 1 except for crossover of the tsDCS dosage. It will also include any clinical testing not completed on day 1.
- 3. Aim 2's pre-test will consist of neuromechanical assessments of walking and reflex testing as well as clinical assessments of pain, spasticity, and physical function.
- 4. 16 sessions of locomotor training will be conducted over 4 weeks with one of the two dosages of tsDCS applied during the training.
- 5. Aim 2's post-test will repeat the measures completed at pre-test.

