A physical therapist will oversee study procedures. Vital signs, such as blood pressure, heart rate and blood oxygen saturation, will be monitored for safety. Rest breaks will be provided at regular intervals and at any time the participant requests. Participants will be informed that they may choose not to perform any aspect of the study. We will adjust the assessment protocol, outlined below, as needed in response to our participants, such as reducing the assessments due to fatigue or individual tolerance.

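### Aim 1's two-visit crossover states no balancing of the two orders and models no visit effect; balanced blocks plus a visit term would be a cheap, conditional gain in precision (minor)

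*Combined protocol and SAP*

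**What the plan says.** Specific Aims describes Aim 1 in these words: "A random order, double blind cross-over study will be conducted across two test sessions". Study Procedures Overview repeats that "participants will complete two separate testing sessions, presented in random order", at least 48 hours apart. Neither section gives blocking, counterbalancing or an order ratio. The Overview points to a figure ("the testing and intervention procedures of this study will be as follows (see Fig. 1 for details"), which is missing from the copy reviewed.

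The Statistical Plan sets a two-way repeated measures ANOVA for Aim 1: "The within factors will be time (before or at the end of walking bout) and stimulation (higher or lower dosage tsDCS"). The time-by-stimulation interaction at p<.05 is the test of interest. No visit (period) or order term is named. The section also says that sample size and the distribution of the data will steer the analysis. That leaves room to change the model but does not plan a visit term.

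On the visits themselves, the Overview says that Aim 1's "first visit will consist of clinical testing and collection of basic demographic information". Visit 2 has "identical procedures for stimulation and neuromechanical assessments as compared to visit 1 except for crossover of the tsDCS dosage", and "It will also include any clinical testing not completed on day 1". Recruitment aims for 20 enrolled and needs at least eight completers.

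**The concern.** In a two-period crossover each dosage is tied to a visit within a person. If the before-to-end change tends to differ between visits for reasons other than dosage, that difference enters each person's dosage contrast, with a sign set by the order. With unbalanced orders it does not average out in the sample at hand. With balanced orders and no visit term it stays in the error term and widens the interval.

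There is some reason to expect such an effect. Clinical testing falls mainly at visit 1. Possible Discomforts and Risks notes that testing can cause fatigue, and Neuromechanical assessments of walking allows the stimulated walk to be adjusted for fatigue. In a study this small, lost precision is worth avoiding when avoiding it costs little.

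**Working it through.** The documents give no SD, effect size, power target or visit effect, so there is no stated figure to reproduce.

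**Inputs.** N = 20 (target) and N = 8 (minimum), from Recruitment. Alpha is 0.05, from the Statistical Plan; two-sided is assumed. Also assumed are 80% power when there is no visit effect, and a visit effect P of 0.25, 0.5 or 1. P is the visit 2 minus visit 1 difference in the before-to-end change, in SDs of the within-person contrast.

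**Step 1: what the planned test is.** For each person let d = (change at the higher dosage) − (change at the lower dosage). With two levels per factor, the interaction test is a one-sample t-test on d with N−1 df. A constant visit shift is present both before and at the end of the walk, so it cancels.

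**Step 2: model.** d = τ ± P + e, with SD(e) = 1. The sign is + if the higher dosage falls at visit 2 and − if it falls at visit 1. The effect giving 80% power at P = 0 is τ = 0.660 (N=20) and 1.156 (N=8).

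**Step 3: independent random order, no visit term.** The mean sign is zero, so the estimate is unbiased over the randomisation. Its variance is (1+P²)/N.
- P=0.25: 1.0625, SE ×1.03; 20/1.0625 = 18.8 effective participants.
- P=0.5: 1.25, SE ×1.12; 20/1.25 = 16.
- P=1: 2.00, SE ×1.41; 20/2 = 10.

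In one realised split the shift is P(n1−n2)/N. At P=0.5, a 12:8 split gives 0.5×4/20 = 0.10 SD and a 14:6 split gives 0.5×8/20 = 0.20 SD.

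**Step 4: visit term.** SE = √((1/n1+1/n2)/4), with N−2 df.
- 10:10: √(0.2/4) = 0.2236; 0.660/0.2236 = 2.95 on 18 df; power 79.8%.
- 12:8: SE 0.2282; power 78.1%.
- 4:4: √(0.5/4) = 0.3536; 1.156/0.3536 = 3.27 on 6 df; power 77.7%.
- 5:3: power 75.1%. 6:2: power 65.8%.

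**Step 5: power (%), by simulation for the planned test and noncentral t for the visit term.**

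| N | Orders | Analysis | P=0 | P=0.25 | P=0.5 | P=1 |
|---|---|---|---|---|---|---|
| 20 | random | planned | 80 | 78 | 71 | 50 |
| 20 | balanced | planned | 80 | 78 | 72 | 49 |
| 20 | random | visit term | 78 | 78 | 78 | 78 |
| 20 | balanced | visit term | 80 | 80 | 80 | 80 |
| 8 | random | planned | 80 | 78 | 71 | 49–50 |
| 8 | balanced | planned | 80 | 78 | 71 | 47 |
| 8 | random | visit term | 71 | 71 | 71 | 71 |
| 8 | balanced | visit term | 78 | 78 | 78 | 78 |

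The type I error of the planned test stays at about 5% under random order. With balanced orders it falls to about 4.4%, 3.0% and 0.6% as P rises (N=20), which shows the visit effect sitting in the error term.

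**Step 6: break-even.** With balanced orders the visit term gains power only above P of about 0.08 at N=20 and about 0.26 at N=8.

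**The case against.** The strongest reply is that nothing here is an error. Order is random, the visits are at least 48 hours apart, and the analysis uses change within a visit. A reader might infer that omitting a visit term biases the estimate or invalidates the p-value. It does neither: averaged over random order the estimate is unbiased with about 5% error. This part of the reply stands in full.

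A reader might also infer that the heavier clinical testing at visit 1 shows a visit effect. It does not. The stimulation and gait procedures are the same at both visits, leftover clinical testing can move to visit 2, and "Rest breaks will be provided at regular intervals and at any time the participant requests". No section says whether clinical testing comes before or after the stimulated walk. Fatigue would also have to alter the change during the walk, not just its starting level. The effect is plausible and no more.

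Three further points stand.
- P = 1 is extreme: at N=20 it exceeds the assumed stimulation effect of 0.66 SD, so the 50% power figure should not be taken as likely.
- Eight is a floor for the whole pilot. The compensation total (2×$20 + 2×$20 + 16×$10 = $240) indicates that the same people do both aims, and the Aim 1 visits come before training. People lost during training still count for Aim 1, so N=8 is a lower bound there.
- Neither half of the fix does the whole job. Balancing alone moves the planned test by under 2 points at N=20. The visit term alone at N=8 loses about 6 points at P=0.25.

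What remains is a real gap in the readable text. The sentence allowing the data to steer the analysis does not fill it, because a visit term is best fixed before outcomes are seen.

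**Conclusion.** Minor: a conditional gain in precision, not a correction of an invalid test. At N=20 the gain over the plan as written is about 2 power points at P=0.25 (78% to 80%) and about 9 at P=0.5 (71% to 80%). At N=8 with a 4:4 split it is nil at P=0.25 and about 7 points at P=0.5 (71% to 78%). With no visit effect there is a small loss.

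These sizes rest on the assumed visit effect, the assumed 80% starting power and a two-sided 5% test. The absence of balancing is established only for the readable text; Fig. 1 might state it.

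**What to change.** 1. Allocate the two orders in small balanced blocks, or, if this is already done, say so.
2. Add visit as a fixed effect in the Aim 1 model of within-visit change. Equivalently, average the two order-specific mean differences in change.
3. State in advance, by order counts only and never by outcomes, when the planned test stays the main analysis with the visit-adjusted estimate beside it. One example is fewer than 10 people completing both Aim 1 visits, or the smaller order holding under 40% of them. At N=20 the 40% limit is a 12:8 split, where the visit term still has about 78% power.

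The cost is a blocked order list, a sentence or two in the Statistical Plan and one degree of freedom. If there is no visit effect and orders are balanced, power goes from 80% to about 79.8% at N=20 and to about 78% at N=8. Blocking at enrolment does not guarantee balance among completers, which is why the third step is needed. At N=8 the term should not be added without blocking.

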#### 3. Abstract:

Locomotor training is a well-established rehabilitation strategy that promotes walking recovery after ISCI. A primary objective of this approach is to promote recovery of spinal locomotor circuitry through excitation from descending motor signals and afferent somatosensory inputs to the spinal cord. 5,6 Following locomotor training, individuals with ISCI often demonstrate improved walking function. 1,3,7,8 However, most people with ISCI continue to have serious walking impairments that limit mobility, community participation and quality of life. A key limitation of current rehabilitation approaches, including locomotor training, is insufficient excitation of spinal locomotor circuitries. 6,10,11 Excitation is needed to drive neuroplastic recovery. Since the majority of SCIs are incomplete, a promising strategy to promote spinal excitation is to use adjuvant approaches that leverage spared pathways and the intact afferent pathways below the level of the lesion. 5,12,13 Transcutaneous spinal direct current stimulation (tsDCS) is a neuromodulatory approach that uses mild and non-invasive electrical stimulation. 14,15 tsDCS induces immediate and lasting changes in spinal cord excitability 14,16-18 and alters reflexive and voluntary behaviors in rodents. 19 Likewise, in humans, tsDCS modulates spinal reflexes, increases corticospinal excitability, and increases motor unit recruitment. Although ample mechanistic evidence suggests that tsDCS could substantially enhance the therapeutic effect of locomotor rehabilitation, this combinatorial approach has not been evaluated in humans with SCI. We propose a proof-of-concept study to investigate the effects of tsDCS on locomotor function and rehabilitation outcomes in individuals with ISCI. The immediate effects of tsDCS will be examined by testing changes in muscle activation, walking kinematics and spinal reflex excitability after a single period of tsDCS application. Furthermore, we will test the hypothesis that tsDCS applied during a regimen of locomotor training will improve the functional walking

outcomes achieved. Results of this pilot project may contribute to the development of a combinatorial rehabilitation strategy that leverages current best practice and a novel non-invasive neuromodulation approach to enhance recovery of walking after ISCI.

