#### 6. Research Plan:

#### Recruitment

A minimum of eight individuals are required to complete this pilot study. We aim to screen 30 individuals and enroll 20 subjects in this study. The target population will be

individuals with SCI. Study procedures will take place at Brooks Rehabilitation, which includes a clinical research facility directed by [name] (Principal Investigator). Potential participants will learn about the study and be recruited in the following primary ways:

- Local advertisements or study flyers (see Recruitment Methods attachments
  for study flyer and email script for potential participants). Individuals may
  contact study personnel at Brooks Rehabilitation. Study staff will be available
  to answer any questions and if the potential participant is interested, the
  individual will be screened for eligibility (screening process detailed below).
- 2. Health care providers at Brooks Rehabilitation or other clinics in the north Florida area (e.g. physicians, physical therapists, or occupational therapists) (see Recruitment Methods attachments for email script for healthcare providers). Health care providers may ask potential participants if they would like to learn more about a current research study. If interested, the potential participants will be provided with a flyer, which will contain instructions for contacting the study staff at the Brooks Rehabilitation Motion Analysis Center. Study staff will be available to answer any questions and if the potential participant is interested, the individual will be screened for eligibility.
- 3. Additionally, the health care provider may ask the potential participant if they are interested in being contacted by a study staff member regarding this research study (see Recruitment Methods attachments for authorization to release patient information form). If written authorization is provided by the potential participant, the health care provider will request his/her name, telephone number, and email address in order to be contacted by the study staff directly. This recruitment strategy will be necessary to help facilitate communication between the potential participant and the study staff. Study staff will contact the potential participant and answer any questions. If the potential participant is interested, the individual will be screened for eligibility.

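### Optional improvement: prespecify baseline adjustment for the Aim 2 walking outcomes; the planned interaction test is valid but leaves chance baseline imbalance unadjusted

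*Combined protocol and SAP*

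**What the plan says.** All references are to the combined protocol and SAP.

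- **Section 5, Specific Aims (Aim 2):** "Primary functional outcomes will include standardized clinical tests of walking speed and endurance". The instruments are not named there. The Clinical assessments section lists the 10MWT (forward speed), the 6MWT (endurance) and also a 3-metre backward walk test.
- **Statistical Plan:** "For Aim 2, mixed method ANOVAs will be used to determine the effects of tsDCS dosage during locomotor training". The factors are set out as follows: "The within factor will be time (pre- or post-test) and between factor will be group (higher or lower dosage tsDCS". The test of interest is then given: "We will then examine the interaction effect to determine differences in the improvement during locomotor training with the two dosages of tsDCS". Significance is set at p<.05, and the ANOVAs apply if data assumptions are met.
- **Statistical Plan, on choice of method:** "Sample size and data distribution will guide statistical analysis". No rule follows.
- **Study Procedures Overview:** Aim 2 has one assessment before and one after the 16 sessions. Assessments may be cut back for fatigue or tolerance.
- **Recruitment:** "A minimum of eight individuals are required to complete this pilot study", and "We aim to screen 30 individuals and enroll 20 subjects in this study".

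The pre-test value is nowhere used as a covariate. The documents give no pre-post correlation, SD, effect size, power or allocation ratio.

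**The concern.** The group-by-time interaction is the only planned test of dosage on the primary walking outcomes. With two time points it compares mean change between arms, which fixes the slope of post-test on pre-test at 1. If the true slope is not 1, the estimate in a given trial moves with whatever baseline difference randomisation happened to produce. With 8 to 20 participants, sizeable differences are common. ANCOVA estimates the slope from data the trial already collects, and so removes that shift if the slope is roughly linear and the same in both arms.

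At stake is how far the observed walking result can be separated from a chance difference in starting function. The open sentence on what will guide the analysis does not settle whether, or when, adjustment would be used.

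**Working it through.** **Nothing to reproduce.** The plan gives 8 and 20 participants but no effect size, SD or power.

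**Assumptions.** Normal data, a common linear slope, two-sided 5% tests, 1:1 allocation unless stated. Pre-test SD = 1, post-test SD = k, pre-post correlation = r, N = completers. Since r and k are not given, r is varied over 0.5-0.95, with k = 1 or 1.2.

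**1. Identity.** In a simulated set of 10 per arm, the interaction F and the squared change-score t were both 0.27886 (p = 0.604, 18 error df).

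**2. Chance imbalance.** P(imbalance of at least 0.5 SD) = 2 × [1 - Φ(0.5/√(1/n1 + 1/n2))].
- 10:10: 0.5/√0.2 = 1.118, giving 26%.
- 8:8: 0.5/√0.25 = 1, giving 32%.
- 4:4: 0.5/√0.5 = 0.707, giving 48%.

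**3. Effect of imbalance on the planned estimate.** The shift is -(1 - kr) per pre-test SD of imbalance. For 0.5 SD at k = 1, r = 0.5, its size is 0.5 × 0.5 = 0.25 SD; at r = 0.9 it is 0.5 × 0.1 = 0.05 SD.

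**4. Variances.**
- Change score: (1/n1 + 1/n2)(1 + k² - 2kr).
- ANCOVA: (1/n1 + 1/n2) k²(1 - r²)[1 + 1/(N-4)].

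Because 1 + k² - 2kr = k²(1 - r²) + (1 - kr)², the ratio ANCOVA/change cannot exceed 1 + 1/(N-4), and reaches it only at kr = 1. The bound is 1 + 1/16 = 1.0625 at N = 20, 1 + 1/12 = 1.083 at N = 16, and 1 + 1/4 = 1.25 at N = 8. Example at N = 20, k = 1, r = 0.5: 0.75 × 1.0625 / 1 = 0.797.

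**5. Simulated consequences.** Power change is ANCOVA minus planned test, in percentage points, with the effect set so that the planned test has 60% power. RMSE (planned / ANCOVA) is in trials with at least 0.5 SD imbalance, N = 20. Shift is the absolute shift for 0.5 SD imbalance.

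| k | r | Shift | Variance ratio, N=20 | RMSE, N=20 | Power change, N=20 | N=16 | N=8 |
|---|---|---|---|---|---|---|---|
| 1 | 0.5 | 0.25 | 0.797 | 0.538 / 0.420 | +9.8 | +8.8 | +1.6 |
| 1 | 0.7 | 0.15 | 0.903 | 0.392 / 0.347 | +4.2 | +3.4 | -3.4 |
| 1 | 0.8 | 0.10 | 0.956 | 0.306 / 0.290 | +1.8 | +1.0 | -5.6 |
| 1 | 0.9 | 0.05 | 1.009 | 0.209 / 0.212 | -0.5 | -1.3 | -7.7 |
| 1 | 0.95 | 0.025 | 1.036 | 0.144 / 0.151 | -1.5 | -2.5 | -8.8 |
| 1.2 | 0.5 | 0.20 | 0.925 | 0.552 / 0.504 | +3.3 | +2.5 | -4.7 |
| 1.2 | 0.7 | 0.08 | 1.027 | 0.402 / 0.415 | -1.2 | -2.3 | -8.3 |
| 1.2 | 0.8 | 0.02 | 1.059 | 0.324 / 0.350 | -2.4 | -3.4 | -9.7 |
| 1.2 | 0.9 | 0.04 | 1.038 | 0.241 / 0.254 | -1.7 | -2.6 | -8.7 |
| 1.2 | 0.95 | 0.07 | 0.932 | 0.197 / 0.182 | +2.8 | +2.0 | -4.8 |

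Worst-case power loss (kr = 1), from 60% planned power: 2.7 points at N = 20, 3.5 at N = 16, 9.8 at N = 8. From 80%: 2.6, 3.5 and 10.5.

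**6. Type I error.** Overall it was 4.9-5.1% for both tests in every setting. Among trials with at least 0.5 SD imbalance at N = 20, the planned test's rate was 9.4% at r = 0.5 and 5.4% at r = 0.95 (k = 1), against about 5% for ANCOVA; it was correspondingly lower in the remaining trials.

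**The case against.** The strongest reply is that there is no defect. The interaction answers the question the plan poses, about differences in improvement, and holds its 5% level. The study is described as proof-of-concept ("We propose a proof-of-concept study to investigate the effects of tsDCS on locomotor function and rehabilitation outcomes in individuals with ISCI") and as a pilot. Choosing between two valid analyses of a randomised comparison is partly preference. All of that stands, and it is why the point is only optional.

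It is also true that ANCOVA does not win throughout. At 20 completers, 5 of the 10 settings favour the planned test on power, and the same five favour it on RMSE even among imbalanced trials only. The same five favour it at N = 16 (for example RMSE 0.359 against 0.393 at k = 1.2, r = 0.8). That stands too, although the gains at N = 20 reach 9.8 points and the losses at most 2.4.

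A rule on completers alone can therefore pick the weaker test in either direction. What it does control is the size of the possible loss, because the bound depends only on N. With r and k unknown, that is the one quantity that can be fixed in advance. Twenty is the enrolment target and not a number of completers, so the rule must also cover smaller numbers.

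One might read the sentence on sample size and data distribution as already permitting adjustment. It permits almost anything and prespecifies nothing.

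**Conclusion.** An optional, inexpensive improvement and not an error. The planned test is valid but does not adjust for the imbalance that occurs. Prespecified adjustment protects against it at a variance cost of at most 6.25% at 20 completers and 8.3% at 16. At 8 completers the ceiling is 25%, and the planned test should stay primary.

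Three stronger readings are not supported:

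- **That the planned analysis is biased or inflates type I error.** Over all randomisations it does neither. The 9.4% applies only to a subset of trials selected for imbalance, under one assumed correlation.
- **That ANCOVA would be more precise or more powerful here.** The documents give neither r nor k. The range at 20 completers is about +10 to -2.5 points, and the even split of settings reflects the grid chosen, not a probability.
- **That a cut-off on completers ensures the better test.** It only limits the loss.

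The result rests on normal data and a roughly linear slope common to both arms, which samples of this size can hardly check.

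**What to change.** Add to the Statistical Plan, before any Aim 2 outcome is analysed by group:

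> For the Aim 2 primary outcomes [name the instruments; the Clinical assessments section suggests the 10MWT and the 6MWT], the post-test value is modelled on dosage group with the pre-test value as covariate, and the adjusted difference and 95% CI are reported. This is the primary analysis for both outcomes if at least 16 participants have pre-test and post-test values on both tests; otherwise the mixed-ANOVA interaction is primary for both. The other analysis is reported as a sensitivity analysis. The condition on data assumptions in this plan applies to both.

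Naming the instruments matters because more than one walking-speed test is listed. The joint count matters because individual assessments may be dropped, which could otherwise give the two outcomes different primary models. The cut-off of 16 is a judgement: it holds the worst-case power loss to about 3.5 points.

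The cost is a few sentences and no new data. The downside is a small loss of power if kr is near 1, and reliance on the common-slope assumption. Secondary outcomes can stay as planned.

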#### Clinical assessments

Clinical assessments will be used to characterize the participants during Aim 1 and to examine changes following the regimen of locomotor training in Aim 2. These assessments will include:

[figure not shown]
- Spinal Cord Assessment Tool for Spastic Reflexes (SCATS)- The SCATS is a reliable and valid tool for assessing spasm activity of flexor and extensor muscle groups as well as spastic hypertonia in patients with spinal cord injury.
- 10-Meter Walk Test (10MWT)- This validated measures assesses forward walking speed.
- 6-Minute Walk Test (6MWT)- The 6MWT is a reliable and valid tool for assessing walking endurance.

- International Standards for the Neurologic Classification of Spinal Cord Injury (ISNCSCI)- Clinical tests of sensory and motor function to classify level and severity of spinal cord injury (ASIA impairment scale)
- 30-second Chair Stand Test (30-s CST)- Performance assessment to measure functional lower limb muscle strength used to move from sitting to/from standing
- Activities Specific Balance Confidence (ABC) Scale- Questionnaire to assess self-reported balance confidence in varied functional situations such as walking in a parking lot or in the home
- Neuromuscular Recovery Scale (NMRS)- Performance assessment of functional motor recovery such as sitting and standing function
- 3-meter Backward Walk Test- An assessment of backward walking speed
- Postural muscle strength assessment Seated clinical test of postural muscle strength using hand-held force dynamometry

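### Does the single p<.05 rule need a ranking of outcomes, given that Aim 2's two primaries are unranked and Aim 1 names no primary?

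*Combined protocol and SAP*

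**What the plan says.** The Statistical Plan section is one paragraph. For Aim 1 it specifies a two-way repeated-measures ANOVA (time by dosage), and for Aim 2 a mixed ANOVA (time within participants, dosage group between). In both it names the interaction as the term to examine. It closes with the threshold: "Differences will be considered significant at p<.05". It says nothing about multiplicity.

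The outcomes are in section 5, Specific Aims.

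- **Aim 2** has two tiers: "Primary functional outcomes will include standardized clinical tests of walking speed and endurance" and "Secondary outcomes will include quantifying changes in muscle activation amplitude and timing", the latter followed by kinematics and cortical control. The primaries are not ranked, and there is no either-or-both rule. Under Clinical assessments, the 10-Meter Walk Test measures forward walking speed, and "The 6MWT is a reliable and valid tool for assessing walking endurance".
- **Aim 1** hypothesises that "tsDCS applied during walking will improve muscle activation and lower limb kinematics in adults with chronic ISCI". It continues: "Outcomes will be changes in muscle activation amplitude and timing, and hip joint excursion during walking". The H-reflex is assessed as well. None of these is called primary.

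On the study's purpose, the Abstract says "We propose a proof-of-concept study to investigate the effects of tsDCS on locomotor function", and Recruitment says "A minimum of eight individuals are required to complete this pilot study". The enrolment target is 20. No power calculation or family-wise error rate is stated.

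**The concern.** Both aims are worded as hypothesis tests and the plan sets a significance threshold, so a reader expects to learn which result decides each hypothesis. The plan fixes the model term but not the outcome. With two Aim 2 primaries and at least three Aim 1 outcomes each tested at .05, the investigators could find one significant result by chance and report it as support for the hypothesis. Nothing written beforehand would say whether one was enough.

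The exposure looks larger for Aim 1. The EMG system has 16 channels, recording is bilateral, and no muscle, leg or summary measure is singled out. With as few as eight completers, a chance result could be over-read. What is at stake is the credibility of a positive statement at the end of the study. No estimate is biased by the omission.

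**Working it through.** **Inputs.** Per-test threshold .05 (Statistical Plan). Two Aim 2 primaries and three listed Aim 1 outcomes (Specific Aims). Sample size 8 to 20 (Recruitment). The documents give no correlations between outcomes, so 0, 0.5 and 0.9 are assumptions. Equal groups (4 or 10 each) and one summary test per outcome are also assumed. The plan states no error rate across outcomes, so there is no figure of its own to reproduce.

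**Step 1: differences in either direction.** For k independent tests the chance of at least one false positive is 1 - 0.95^k.

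- k = 2: 1 - 0.95² = 0.0975
- k = 3: 1 - 0.95³ = 0.1426
- k = 4 (adding the H-reflex): 1 - 0.95⁴ = 0.1855

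Correlation lowers these figures. From the multivariate normal, P(any |z| > 1.96):

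| Outcomes | r = 0 | r = 0.5 | r = 0.9 |
|---|---|---|---|
| 2 | 0.0975 | 0.0907 | 0.0704 |
| 3 | 0.1426 | 0.1254 | 0.0836 |

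**Step 2: improvement only.** Each hypothesis says that stimulation will improve something, so only a result in the favourable direction supports it. A two-sided .05 test gives a false claim of improvement 2.5% of the time. For independent outcomes the formula becomes 1 - 0.975^k: 1 - 0.975² = 0.0494 and 1 - 0.975³ = 0.0731.

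| Outcomes | r = 0 | r = 0.5 | r = 0.9 |
|---|---|---|---|
| 2 | 0.0494 | 0.0454 | 0.0352 |
| 3 | 0.0731 | 0.0627 | 0.0418 |

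For Aim 2, where faster or farther is plainly better, the improvement-only row for two outcomes is the relevant one: 3.5-4.9%. For Aim 1 the favourable direction of a change in activation amplitude or timing is not defined, so the two-sided row for three outcomes is the fairer guide: 8.4-14.3%.

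**Step 3: small samples.** With two time points, the Aim 2 interaction test is a two-sample t-test on change scores, and the Aim 1 interaction test is a one-sample t-test on within-person differences. Simulation gives nearly the same rates.

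- Aim 2, either primary, two-sided, r = 0 / 0.5 / 0.9: 0.099 / 0.093 / 0.073 with 4 per group; 0.098 / 0.091 / 0.071 with 10 per group.
- Aim 2, improvement only: 3.6-5.0% over the same range.
- Aim 1, any of three, two-sided: 0.141 / 0.130 / 0.089 with 8 participants; 0.142 / 0.126 / 0.087 with 20.

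**Step 4: what a stricter rule would cost.**

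- *Both Aim 2 primaries required.* If each test alone has 80% power (a true difference of 1.325 SD of change, 10 per group), power falls to 0.640 / 0.685 / 0.746 at r = 0 / 0.5 / 0.9.
- *Holm.* The first step is at .025. For one outcome held to that level, the difference detectable with 80% power rises from 1.325 to 1.484 SD with 10 per group, and from 2.381 to 2.787 SD with 4 per group. That overstates the cost when either outcome suffices: at 1.325 SD on both, the chance that at least one passes is 91% / 85% / 76% at r = 0 / 0.5 / 0.9, against 80% for a single test.
- *Fixed order.* The first outcome loses no power, but someone must choose which outcome goes first, and a result seen only on the second drops to exploratory.

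**The case for a change.** The best argument for a change is that it needs only wording. A plan that sets a threshold and speaks of testing hypotheses should say what decides them, and naming one primary per aim would settle it without adding a visit or a participant. Being a pilot does not answer this fully, because pilots are also reported with p-values and a chance finding in eight people is easy to over-read.

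The argument is strongest for Aim 1. Three outcomes is a low count: the H-reflex takes it to four (18.6% if independent), and separate tests by muscle or side would raise it further; eight independent tests, an illustrative number, would give 33.7%. Even for Aim 2, 3.5-4.9% is 1.4 to 2 times the 2.5% of a single test (3.5/2.5 = 1.4; 4.9/2.5 ≈ 2.0).

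What stands is that the omission is real, and that an isolated significant Aim 1 result should be read as a lead to follow up. What does not stand is that the plan breaches its own error rate. It sets a threshold for each difference, and each interaction test is held to that threshold. Nor is there one evident remedy. One primary, a fixed order, both required, Holm, or treating all p-values as exploratory are each defensible here, and they lead to different claims.

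**Conclusion.** No change to the plan follows. No rule across outcomes is written down, but the consequence is modest and visible. Aim 2 already separates primary from secondary outcomes, its two primaries correspond to two recognisable walking tests, and even the loosest reading keeps the chance of a false claim of improvement at about 5% or less (3.5-4.9%; up to 5.0% in small-sample simulation). If both primaries are expected to move, there is no inflation at all.

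Aim 1 is looser at 8.4-14.3%, but it examines immediate, mechanism-oriented effects in a proof-of-concept study on which no confirmatory claim rests. Analysts can deal with the gap sensibly when reporting: show the interaction estimate for every listed outcome and present a lone significant result as one of several tested. Imposing a family-wise rule would be a trade-off, since requiring both Aim 2 primaries takes power from 80% to 64-75% in a study of at most about 20 people.

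These figures assume correlations between 0 and 0.9, equal groups and one summary test per outcome; the Aim 1 figure would be higher if several muscles or legs were tested separately. The conclusion also assumes that the study is reported as the pilot it describes. If a significant result on one selected outcome were presented as confirmation, the concern would return, as a fault of the report.
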